2.1.3 Supportive Clinical Data

The Phase 1 Study UBX0101-OAR-101 (NCT03513016) represents the clinical experience to date with UBX0101 administered by IA injection. The study population was adults age \geq 40 to \leq 85 years with moderate to severe, painful knee OA.

In Part A, the single ascending dose portion of the study evaluating six dose levels of UBX0101 (between 0.1 and 4 mg), 48 patients were randomly assigned to receive UBX0101 or placebo. Primary endpoints were safety and tolerability. Secondary and exploratory endpoints included plasma PK, synovitis as measured by MRI, pain (as measured by WOMAC-A and NRS), and measurement of SASP factors and disease-related biomarkers present in synovial fluid and plasma.

In Part B, 30 patients were to receive a single-dose IA administration of UBX0101 (4.0 mg) or placebo in a 2:1 randomization. Primary endpoints were safety and tolerability. Secondary and exploratory endpoints included changes in the levels of SASP factors and disease-related biomarkers present in synovial fluid and plasma as well as pain at 4 weeks only. Synovial fluid samples were obtained at baseline and 4 weeks post-treatment.

In the Phase 1 study, single doses of UBX0101 IA up to 4 mg administered to patients with painful knee OA were found to be safe and generally well tolerated. During the study, 65 adverse events (AEs) were reported by 36 out of 78 patients (56 AEs in 28 patients in Part A

and 9 AEs in 8 patients in Part B). Most AEs were rated as mild in intensity. No dose-dependent pattern of AEs was observed. There were no serious adverse events (SAEs) and no AEs that led to discontinuation.

In Part A, 7 AEs considered related to Study Drug were reported in 6 patients: procedural pain (placebo-treated patient), arthralgia (0.4 mg dose patient), muscle spasms (0.4 mg dose patient), OA (1.0 mg dose patient), procedural pain and synovitis (both in one 2.0 mg dose patient), and post-procedural swelling (4.0 mg dose patient). In Part B, 3 AEs considered related to Study Drug were reported in 2 patients: procedural pain and joint effusion (both in the same 4 mg dose patient) and procedural pain (4.0 mg dose patient). No clear dose dependence of causally related AEs was observed in this Phase 1 study.

In terms of clinical responses, patients treated with single IA injections of UBX0101 had clinically meaningful and dose-dependent improvements in knee pain symptoms as measured by the average daily pain NRS (0–10 point scale) and the WOMAC-A (Likert scale, 0–4) at 12 weeks compared to those who received placebo treatment. In a prospectively defined analysis in which the placebo (n = 14), low dose combined 0.1 through 0.4 mg UBX0101 (n = 16), and high dose combined 1 through 4 mg UBX0101 (n = 18) groups were compared, the least squares (LS) mean of the change from baseline (CFBL) in NRS at Week 12 was significantly greater for the high dose UBX0101 group (-3.95, p < 0.01) compared to the placebo (-1.96) and low dose groups (-2.66, p = 0.42 versus placebo). Especially for the UBX0101 4 mg highest dose group, LS mean reductions from baseline in the NRS of 4 points and greater up to Week 12 suggested a large magnitude UBX0101 treatment effect. Similarly, pain reduction as measured by WOMAC-A was clinically meaningful and greater in the high dose UBX0101 group compared to the placebo and the low dose groups. For the higher doses, the pain responses appeared to be durable through 12 weeks. The improvements in pain NRS over time in Part A are presented in Figure 2.

[figure not shown]

Figure 2 NRS Weekly Least Squares Mean Change From Baseline to Week 12

CFBL=change from baseline; LS=least squares; NRS = numeric rating scale; SE=standard error.

Clinically meaningful, dose-dependent improvements in physical function as measured by the Western Ontario and McMaster Universities Osteoarthritis Index function subscale (WOMAC-C) were observed and were greater in UBX0101-treated patients compared to those who received placebo. Evaluation of Patient Global Impression of Change (PGIC) following UBX0101 treatment demonstrated a higher proportion of patients being "much improved" or "very much improved" versus placebo at 12 weeks (placebo = 42.9%, low doses of UBX0101 [0.1, 0.2, and 0.4 mg] = 50.0%, high doses of UBX0101 [1.0, 2.0, and 4.0 mg] = 61.1%).

In Part B, the UBX0101 4.0 mg treatment group (n = 20) had a numerically greater mean reduction in WOMAC-A at 4 weeks compared to the placebo group (n = 10), but this was not statistically significant. The different magnitudes of treatment effect on WOMAC-A for the UBX0101 4.0 mg groups in Parts A and B may be due to factors including different study designs, study cohorts and investigative sites, frequency and timing of pain reporting, and the focus on arthrocentesis and lavage procedures to collect synovial fluid in Part B.

In Part B, 19 biomarkers were analyzed across 20 matched, paired synovial fluid samples. In approximately half the biomarkers measured in synovial fluid (treatment versus placebo) modulation was observed consistent with elimination of SnCs and potential improvement in the tissue environment. Changes were observed in matrix metalloproteases, tissue remodeling factors, and inflammatory cytokines.

In summary, single doses of UBX0101 up to 4.0 mg were safe and well-tolerated in patients with knee OA. Dose-dependent clinical responses in patient-reported measures of pain and function,

and UBX0101 treatment resulted in modulation of multiple biomarkers in the synovial fluid. Together, these results are encouraging, and suggest that a senolytic drug can at the same time address both symptoms of knee OA and the pathophysiology of structural progression.

2.1.4 Benefit:Risk Assessment

As described in Section 2.1, despite the major potential for progressive disability associated with OA, all presently available treatments for the disease are symptomatic and focus on pain management, such as analgesics and anti-inflammatory agents, and have essentially no impact on its inevitable progression. UBX0101, a MDM2/p53 inhibitor, intervenes in the disease pathogenesis of OA by inducing apoptosis of SnCs within tissues of the knee, thus reducing the production of pro-inflammatory, ECM-modifying, and regeneration-suppressing factors. As such, UBX0101 intervention in OA pathogenesis may ultimately halt or potentially reverse joint degeneration.

In the Phase 1, first-in-human study (Study UBX0101-OAR-101), single doses of 0.1 mg up to 4.0 mg UBX0101 administered as IA injections into the target knee joint were well tolerated in patients with OA up to and including a dose of 4.0 mg. There were neither SAEs nor AEs that led to study discontinuation. In the overall study population of 78 patients, 65 non-serious AEs were reported in 36 patients; no dose-dependent pattern of AEs was observed. The three highest doses of UBX0101 (1, 2, and 4 mg) resulted in clinically meaningful improvements in pain and physical function compared to placebo as measured by the 11-point NRS, WOMAC-A, and WOMAC-C. Additionally, the improvements in WOMAC-A and WOMAC-C had rapid onset within 1–2 weeks and were sustained for 12 weeks in the patients treated with UBX0101 1.0, 2.0, or 4.0 mg.

In summary, based on the clinically significant and durable improvements in pain and function observed in the Phase 1 study, coupled with the generally well-tolerated nature of UBX0101 IA injection, the benefit:risk profile is favorable. The Phase 1 results support further evaluation of UBX0101 doses of 0.5, 2.0, and 4.0 mg in a Phase 2 study.

2.2 Study Rationale

Building on the favorable clinical responses and safety results obtained during the Phase 1 study, this Phase 2 study is intended to assess the efficacy, safety, and tolerability of a single-dose IA administration of UBX0101 in moderate to severe painful established femoro-tibial OA.

3 OBJECTIVES AND ENDPOINTS

Objectives and endpoints for this study are listed in Table 2.

 Table 2
 Study Objectives and Endpoints

Tier	Objectives	Endpoints
Primary	Evaluate the effect of IA administration of UBX0101 on the change from baseline to Week 12 of pain in the target knee	Change from baseline to Week 12 of the WOMAC-A score in patients receiving a single 0.5, 2.0, or 4.0 mg dose of UBX0101 versus those receiving placebo
Secondary	Evaluate the effect of IA administration of UBX0101 on the change from baseline to Week 12 in physical function	Change from baseline to Week 12 of the WOMAC-C function subscale score in patients receiving a single 0.5, 2.0, or 4.0 mg dose of UBX0101 versus those receiving placebo
Secondary	Evaluate the effect of IA administration of UBX0101 on the change from baseline to Week 12 in pain reported by patients daily over the 12-week study period	Change from baseline to Week 12 of the weekly mean of the average daily pain intensity scores on the 11-point NRS in patients receiving a single 0.5, 2.0, or 4.0 mg dose of UBX0101 versus those receiving placebo
Secondary	Evaluate the effect of IA administration of UBX0101 on the duration of symptom improvement (pain and function) following IA administration of UBX0101 out to 24 weeks	Change from baseline (over the entire 24-week period, including both the primary study period and the 12-week follow-up period) out to Week 24 for the WOMAC-A, NRS, and WOMAC-C scores in Patients receiving a single 0.5, 2.0, or 4.0 mg dose of UBX0101 versus those receiving placebo
Secondary	Evaluate the safety and tolerability of single-dose IA administration of UBX0101	Incidence of AEs as well as change from baseline through Weeks 12 and 24 in vital signs and selected laboratory safety parameters (as deemed clinically appropriate) in patients receiving a single 0.5, 2.0, or 4.0 mg dose of UBX0101 versus those receiving placebo
Exploratory	Explore the effects of single-dose IA administration of UBX0101 on the change from baseline in patient reported assessment of their osteoarthritis at the time of inquiry	Change from baseline to Week 12 and to Week 24 in PGA score in patients receiving a single 0.5, 2.0, or 4.0 mg dose of UBX0101 versus those receiving placebo
Exploratory	Explore the effects of single-dose IA administration of UBX0101 on the change from baseline in patient reported impression of how their osteoarthritis has changed over the course of the study	Endpoint: Change from baseline to Week 12 and to Week 24 in PGIC score in patients receiving a single 0.5, 2.0, or 4.0 mg dose of UBX0101 versus those receiving placebo
Exploratory	Explore the effects of single-dose IA administration of UBX0101 on soluble biomarkers and imaging biomarkers of joint degeneration and repair	Change from baseline out to Week 24 in serum/plasma and urine biomarkers of synovium, cartilage, and bone degeneration Change from baseline to Week 24 in MRI-based markers of joint structure

PGA=Patient Global Assessment; PGIC=Patient Global Impression of Change.

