Exploratory Objectives and Corresponding Endpoints	Objective: Explore the effects of single-dose IA administration of UBX0101 on the change from baseline in patient reported assessment of their osteoarthritis at the time of inquiry Endpoint: Change from baseline to Week 12 and to Week 24 in Patient Global Assessment score in patients receiving a single 0.5, 2.0, or 4.0 mg dose of UBX0101 versus those receiving placebo Objective: Explore the effects of single-dose IA administration of UBX0101 on the change from baseline in patient reported impression of how their osteoarthritis has changed over the course of the study Endpoint: Change from baseline to Week 12 and to Week 24 in Patient Global Impression of Change score in patients receiving a single 0.5, 2.0, or 4.0 mg dose of UBX0101 versus those receiving placebo Objective: Explore the effects of single-dose IA administration of UBX0101 on soluble biomarkers and imaging biomarkers of joint degeneration and repair Endpoints: • Change from baseline out to Week 24 in serum/plasma and urine biomarkers of synovium, cartilage, and bone degeneration					
	Change from baseline to Week 24 in magnetic resonance imaging-based markers of joint structure					
Number of Sites	15–20					
Study Duration	Estimated duration: 13 months					
Safety Assessment Committee	A safety assessment committee will be established for adjudication of AEs or possible safety signals.					

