⁴ Physical examination includes assessments of the skin, head and neck, lungs, heart, abdomen, lymph nodes, extremities, and body weight and will be conducted at Screening and at and Final Follow-up (Visit 8/ Week 24) or Early Termination. Height will be measured at Screening only. After Day 1, symptom-directed physical examinations are required as clinically indicated.

⁵ Knee examination: The target knee will be examined for erythema, palpable warmth, tenderness, swelling, effusion, crepitus, laxity, and range of motion.

⁶ Vital signs include blood pressure, respiratory rate, pulse rate, and oral temperature. Patients will have a 5-minute rest in a sitting position before vital signs are assessed

⁷ 12-lead ECG evaluation will be performed predose for baseline reference.

⁸ Hematology and chemistry: Screening tests in patients with diabetes should include hemoglobin A1c. If the Investigator deems appropriate, patients will be permitted to retest on clinical laboratory tests once while they are within the Screening window.

⁹ Visit 8 MRI may be performed 14 days prior to Visit 8 to allow for scheduling flexibility.

¹⁰ Dose will be administered using ultrasound guidance at Visit 1/Week 0/Day 1.

¹¹ All questionnaires will be conducted prior to vital signs, physical exams, ECGs, and blood draws. The wording and answer options of the PGA and PGIC question are referenced in Appendix 3.

¹² NRS daily pain score will be obtained for a minimum of 5 days during the Screening period to assess baseline pain for eligibility. Patients will complete an average daily pain question every day, from baseline through their last study visit, using an electronic diary. Clinical sites are to monitor ePRO responses at each visit to increase compliance. The NRS daily pain score is referenced in Appendix 2.

¹³ MPsQ will be collected predose at Visit 1/Week 0/Day 1.

¹⁴ PK blood sampling: On Day 1, blood will be drawn for plasma PK assessment at 2 hours postdose with a ±15-minute window.

¹⁵ Blood biomarker samples to yield serum and plasma samples will be collected and processed according to the instructions in the Laboratory Manual.

¹⁶ Urine biomarker samples will be collected and processed according to the instructions in the Laboratory Manual.

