6.1.1.1 Screening Period/Day -35 to -1

- · Obtain informed consent
- Review eligibility criteria
- Record demographics
- Review medical history
- Perform medication review (including concomitant medication)
- Administer WOMAC
- Administer Patient Global Assessment (PGA)
- Perform pregnancy test
- Perform urine drug screen
- Perform physical examination
- Perform knee examination
- Measure vital signs
- Perform laboratory tests (hematology and chemistry)
- Perform knee x-ray
- Perform MRI
- Patients to be trained on completing the NRS Daily Pain question on the e-diary

6.1.1.2 Visit 1/Week 0/Day 1

- Review eligibility criteria
- Review medical history
- Randomization
- Perform medication review (including concomitant medication)
- Administer WOMAC
- Administer PGA
- Administer Multidimensional Psychological Questionnaire (MPsQ)
- Perform physical examination
- Perform knee examination
- Measure vital signs
- Perform ECG
- Perform urine pregnancy test
- Perform laboratory tests (hematology and chemistry)
- Conduct blood biomarker sampling
- Conduct urine biomarker sampling
- Administer study drug
- · Conduct AE assessment
- Conduct pharmacokinetics blood sampling

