6.1.1.7 Visit 6/Week 12/ Day 85 (±10 days)

- Perform medication review (including concomitant medication)*
- Administer WOMAC*
- Administer PGA*
- Administer PGIC*
- · Perform knee examination
- Measure vital signs
- Perform laboratory tests (hematology and chemistry)
- Conduct blood biomarker sampling
- Conduct urine biomarker sampling
- Conduct AE assessment*
- Review NRS Daily Pain response*

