6.1.1.10 Unscheduled Visits and Early Termination

- Perform medication review (including concomitant medication)*
- Administer WOMAC*
- Administer PGA*
- Administer PGIC (Early Termination only)*
- Perform physical examination
- Perform knee examination
- Measure vital signs
- Perform laboratory tests (hematology and chemistry)
- Perform serum pregnancy test
- Conduct blood biomarker sampling

- Conduct urine biomarker sampling
- Conduct AE assessment*
- Review NRS Daily Pain response and de-activate e-diary (Early Termination only)*

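### Does the exploratory PGIC endpoint need redefining because it is worded as a change from baseline that PGIC does not have?

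*Combined protocol and SAP*

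**What the plan says.** Table 2 (Section 3) lists two patient-rated global measures as exploratory. For PGA the endpoint is "Change from baseline to Week 12 and to Week 24 in PGA score". For PGIC it is "Change from baseline to Week 12 and to Week 24 in PGIC score in patients receiving a single 0.5, 2.0, or 4.0 mg dose", compared with placebo. The synopsis has the same PGIC endpoint: "Change from baseline to Week 12 and to Week 24 in Patient Global Impression of Change score". The PGIC objective is phrased in the same way, as a "change from baseline in patient reported impression of how their osteoarthritis has changed over the course of the study".

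The schedule treats the two instruments differently. Section 6.1.1.1 includes "Administer Patient Global Assessment (PGA" at Screening, and Section 6.1.1.2 repeats PGA on Day 1. PGIC is in neither list. It first appears at Week 12 ("Administer PGIC", Section 6.1.1.7), then at Week 24 (Section 6.1.1.9) and at early termination (Section 6.1.1.10). Table 1 agrees that there is no PGIC before dosing.

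Appendix 3 gives the PGIC item in full. It asks the patient to describe the change in the study knee since the Day 1 treatment, on seven verbal categories from very much improved to very much worse, at Weeks 12 and 24.

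**The concern.** A change from baseline is a post-dose value minus a pre-dose value, and PGIC has no pre-dose value. Nor could one sensibly be added, since a question about change since treatment has no meaning before treatment. The objective compounds the problem by asking for the change in an impression of change. Appendix 3 also attaches no numeric codes to the seven categories, so the word score is undefined as well.

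If the endpoint were taken at face value, the protocol would specify a derived variable that cannot exist, and different analysts might fill the gap differently. At stake is the definition of one exploratory endpoint.

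**Working it through.** **1. Which measures have a baseline.** Scheduled assessments counted from Table 1, the visit lists in Section 6.1.1 and Appendix 3, leaving out unscheduled and early termination visits:

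| Measure | Before dosing | After dosing |
|---|---|---|
| WOMAC (A and C) | 2 (Screening, Day 1) | 7 (Weeks 1, 2, 4, 8, 12, 18, 24) |
| NRS | daily diary, at least 5 days | daily diary |
| PGA | 2 (Screening, Day 1) | 2 (Weeks 12, 24) |
| PGIC | 0 | 2 (Weeks 12, 24) |

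The NRS entry rests on footnote 12 of Table 1: "NRS daily pain score will be obtained for a minimum of 5 days during the Screening period to assess baseline pain for eligibility". Of the five patient-reported measures given a change-from-baseline endpoint (WOMAC-A, WOMAC-C, NRS, PGA, PGIC), PGIC alone has no pre-dose value. The literal reading therefore fails for PGIC and only for PGIC.

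**2. What an analyst could do with the wording.** Let R be a patient's PGIC rating at a given visit, on any numeric coding.

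- *Use the rating directly.* The item is anchored to Day 1, so R is the patient's own rating of change from baseline. The comparison is R in each UBX0101 arm against R in placebo.
- *Impute a baseline.* The only natural value is no change for every patient, a constant c. The derived score is R − c. Between arms, (mean R active − c) − (mean R placebo − c) = mean R active − mean R placebo. The constant cancels, and ranks and category proportions are untouched. The result is the same as in the first reading.
- *Treat Week 12 as baseline.* The Week 12 change would then be R − R = 0 for everyone. The endpoint names Week 12 as a time at which change is to be assessed, so its own text rules this reading out.

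The two workable readings give the same comparison between arms.

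**3. Whether any analysis text calls for the impossible difference.** Section 9.1.3 names change from baseline for WOMAC-A, NRS and WOMAC-C only. Section 9.1.4 sends exploratory analyses to the Statistical Analysis Plan, with biomarkers as its example. PGIC is not mentioned anywhere in Section 9.

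**4. How the sponsor has summarised PGIC before.** Section 2.1.3 reports the Phase 1 proportions in the top two improvement categories at 12 weeks as 42.9% (placebo), 50.0% (low doses) and 61.1% (high doses). The same section gives group sizes of 14, 16 and 18. These match whole-number counts: 6/14 = 42.9%, 8/16 = 50.0%, 11/18 = 61.1%. They are plain proportions of post-dose answers, with no baseline involved.

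**5. Effect on the sample size.** Section 9.1.1 uses a WOMAC-A difference of 0.50, SD 0.75, two-sided alpha 0.10 and power 90%. The normal approximation gives n = 2 × (1.645 + 1.282)² × (0.75/0.50)² = 2 × 8.57 × 2.25 ≈ 38.6, so 39 per group. The t-test version gives 39.2, so 40, which matches the plan. With 10% dropout, 40/0.9 = 44.4, so 45 per group and 4 × 45 = 180. No PGIC quantity enters.

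**The case for a change.** The strongest case for a correction is that an endpoint definition should be right as written. The synopsis and Table 2 are the only places in the protocol text that define the PGIC endpoint, and both define it in terms that contradict the protocol's own schedule and questionnaire. Section 9 does not repair this; it only defers to the Statistical Analysis Plan. The correction would be cheap: four phrases, with no new data or visits.

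The factual part stands in full. The wording is wrong, and anyone amending the protocol for another reason could tidy it. What does not stand is the step from there to a needed change in the plan. The risk would be that someone computes something else, or that data are missing when the analysis is run. Appendix 3 removes the second risk by fixing the item, the answers and the times. The first is remote, because the only other workable reading gives the same comparison. The missing numeric codes matter only if a mean score is wanted, and a proportion or an ordinal comparison needs none. Counting the change scores that cannot be formed across all patients and visits adds nothing, since it multiplies the single fact of no baseline by the sample size.

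**Conclusion.** The wording is a clerical slip, apparently copied from the PGA row, in one exploratory endpoint. Analysts will fill the gap sensibly, because the PGIC answer at Week 12 or Week 24 is itself the change since Day 1. Rewording would alter no assessment, dataset, estimate, error rate or conclusion, and the primary and secondary endpoints and the 180-patient sample size are untouched. No change to the plan follows.

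This rests on two assumptions: that PGIC is collected as Table 1 and Appendix 3 describe, and that the detailed analysis compares the post-dose answers between arms, as the Phase 1 summary did. The text available for review contains no PGIC analysis method, so the second cannot be confirmed here. Nothing in that text points the other way.
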